5.2.1 Response Criteria RECIST 1.1

5.2.1.1 Evaluation of target lesions*

- Complete Response (CR): Disappearance of all target lesions. Any pathological lymph nodes (whether target or non-target) must have reduction in short axis to <10 mm.
- Partial Response (PR): At least a 30% decrease in the sum of diameters of target lesions taking as reference the baseline sum diameters.
- Progression (PD): At least a 20% increase in the sum of diameters of target lesions taking as reference the smallest sum on study (this includes the baseline sum if that is the smallest on study) or the appearance of one or more new lesions.

- Stable Disease (SD): Neither sufficient shrinkage to qualify for PR nor sufficient increase to qualify for PD taking as references the smallest sum diameters while on study.

* *All measurable lesions up to a maximum of 5 lesions (and a maximum of 2 lesions per organ) representative of all involved organs should be identified as **target lesions** and recorded and measured at baseline. Target lesions should be selected on the basis of their size (lesions with the longest diameter), be representative of all organs involved, and be suitable for accurate repetitive measurements (either by imaging techniques or clinically). A sum of the diameters (longest for non-nodal lesions, short axis for nodal lesions) for all target lesions will be calculated and reported as the baseline sum diameters. The baseline sum diameters will be used as reference to further characterize the objective tumor response of the measurable dimension of the disease.*

5.2.1.2 Evaluation of non-target lesions **

- Complete Response (CR): Disappearance of all non-target lesions and normalization of tumor marker level. All lymph nodes must be non-pathological in size (<10mm short axis).
- Non-CR/Non-PD: Persistence of one or more non-target lesions and/or maintenance of tumour marker level above the normal limits.
- Progression (PD): Appearance of one or more new lesions. Unequivocal progression of existing non-target lesions

** All other lesions (or sites of disease), including pathological lymph nodes should be identified as **non-target lesions** and should also be recorded at baseline. Measurements are not required, and these lesions should be followed as “present”, “absent”, or in rare cases “unequivocal progression.”

5.2.1.3 Evaluation of best overall response

The best overall response is the best response recorded from the start of the treatment until disease progression/recurrence (taking as reference for progressive disease the smallest measurements recorded since the treatment started). The patient's best response assignment will depend on the achievement of both measurement and confirmation criteria.

Target Lesions	Non-Target Lesions	New Lesions	Overall Response
CR	CR	No	CR
CR	Non-CR/Non-PD	No	PR
CR	Not evaluated	No	PR
PR	Non-PD or not all evaluated	No	PR
SD	Non-PD or not all evaluated	No	SD
Nor all evaluated	Non-PD	No	NE
PD	Any	Yes or No	PD
Any	PD	Yes or No	PD
Any	Any	Yes	PD

5.3 TOXICITY CRITERIA

The following adverse event management guidelines are intended to ensure the safety of each patient while on the study. The descriptions and grading scales found in the revised NCI Common Terminology Criteria for Adverse Events (CTCAE) version 4.0 will be utilized for AE reporting. All appropriate treatment areas should have access to a copy of the CTCAE version 4.0. A copy of the CTCAE version 4.0 can be downloaded from the CTEP web site (http://ctep.cancer.gov/protocolDevelopment/electronic_applications/ctc.htm#ctc_40).

5.4 SAMPLE STORAGE, TRACKING, AND DISPOSITION

Tumor tissue biopsy samples

Patients who have locoregional or metastatic disease that is amenable to ultrasound guided and or CT scan guided needle biopsy will have this done of the target lesion. This will be performed at study entry and at 10 weeks.

Immediate cytopathologic review will be performed to confirm the presence of tumor cells. The samples will then be stored in -80°C until the immunohistochemistry studies and genome-wide gene expression analysis.

The Na/I symporter expression level will be determined by quantitative RT PCR and immunohistochemistry (11-14). Gene expression levels (differentiation *markers*, *cell cycle and apoptosis regulatory genes*) changes with valproic acid treatment will be determine by using pathway specific gene expression arrays (12,13).

Blood samples

The laboratory studies will be blinded to the response of patients to therapy.

Samples will be sent to the Endocrine Oncology Laboratory for processing:

NCI Endocrine Oncology Branch Laboratory
[name]
[name]
[name]
[contact]

At the completion of the protocol, the investigator will dispose of all specimens in accordance with the environmental protection laws, regulations and guidelines of the Federal Government

and the State of Maryland. Any unintentional loss or destruction of the tissue will be reported to the IRB.

6 STATISTICAL CONSIDERATIONS

6.1 RATES AND TYPES OF RESPONSES

Rates and types of responses will be determined and presented with 95% confidence intervals. Patient characteristics (demographic and clinical) will be tabulated. Overall survival will be summarized using Kaplan-Meier curves. Toxicities will be tabulated by grade and organ system. Summary responses to the quality of life instrument at selected time points will be tabulated; to aid in the interpretation of temporal changes in quality of life items, change scores will be evaluated using the Wilcoxon signed rank test or McNemar's test as appropriate.

6.2 SAMPLE SIZE AND POWER ANALYSIS

This is a phase II study aimed at measuring the impact of valproic acid on iodine uptake and on tumor response. Response will be defined as complete or partial response as outlined in section 5.2. The study uses a two-stage Simon optimal design with an interim analysis planned when 13 patients are evaluable for response. If no complete/partial responses are seen at that time the study will close to accrual. The study will proceed to stage II if at least one response is seen among the first 13 patients. At the end of study, if the cumulative number of responses among the 20 evaluable patients is 3 or more, valproic acid will be considered efficacious, while this will not be the case if 1-2 responses are noted. Under the null hypothesis of a true response rate that does not exceed 5% ($p_0=0.05$), the two-stage design will control type I error (α) to be no more than 7.4%, and when the true response rate is at least 25% ($p_1=0.25$), the study has at least 90% power ($\beta=0.10$). The probability of triggering early stopping is at least 51% if the true response rate is 5% or less, and less than 2.5% if the true response rate is 25% or more. If the accrual is stopped at the first stage due to futility, the upper bound of a 95% confidence interval for the response rate will be less than 25%. We will plan to enroll up to 25 patients with the expectation that 20 patients (80%) will be evaluable for response.

The stopping rule for Grade 3 toxicity is set at 15% as the acceptable toxicity rate because the study is designed to detect a treatment efficacy rate of 15% or higher. Therefore, if the acceptable toxicity rate is higher than the expected efficacy rate the study will be stopped.

7 HUMAN SUBJECTS PROTECTIONS

7.1 RATIONALE FOR SUBJECT SELECTION

Subjects from both genders and all racial/ethnic groups are eligible for this study if they meet the eligibility criteria. To date, there is no information which suggests that differences in drug metabolism or disease response would be expected in any one patient group. As advanced

thyroid cancers are rare in the pediatric population, study will not include patients < 18 years of age.

7.2 PARTICIPATION OF CHILDREN

As noted above, children under the age of 18 will not be enrolled.

7.3 EVALUATION OF BENEFITS AND RISKS/DISCOMFORTS

Treatment with valproic acid may prove to be more effective than current conventional therapy (thyroid hormone suppression) for advanced differentiated thyroid cancers. Patients with a long history of unresponsiveness to other treatment modalities (surgical debulking, thyroid hormone suppression, radioactive iodine, external beam radiation) may experience an actual therapeutic benefit. Risks include those associated with the agent, and standard imaging procedures for this disease entity. Care will be taken to minimize side effects, but they can be unpredictable in nature and severity. This study may involve risks to patients, which are currently unforeseeable. All patients will have laboratory tests to monitor for complications. If patients suffer any physical injury as a result of the participation of this study, immediate medical treatment is available at the Clinical Center, National Cancer Institute, Bethesda, Maryland. Although no compensation is available, any injury will be evaluated and treated in keeping with the benefits or care to which patients are entitled under applicable regulations.

7.4 RISKS/BENEFITS ANALYSIS

Patients with differentiated thyroid cancer of follicular cell origin have limited options available to them. Valproic acid is an approved agent for other indications and the toxicities have been well established. The potential benefits of increased ability to diagnosis and treat residual malignancies in this patient population outweigh the risks of treatment with valproic acid. If this study demonstrates a tumor response to valproic acid and/or increased radioiodine uptake in patients who are otherwise no longer amenable to conventional therapy, a large, multicenter, trial using valproic acid in this population of patients will be considered.

7.5 CONSENT AND ASSENT PROCESS AND DOCUMENTATION

The investigational nature and objectives of this trial, the procedures and treatments involved and their attendant risks and discomforts, potential benefits and potential alternative therapies will be carefully explained to the patient, and a signed informed consent document will be obtained by the PI, AI or clinical staff fellow.

8 SAFETY REPORTING REQUIREMENTS/DATA AND SAFETY MONITORING PLAN

8.1 DEFINITIONS

8.1.1 Adverse Event

An adverse event is defined as any reaction, side effect, or untoward event that occurs during the course of the clinical trial associated with the use of a drug in humans, whether or not the event is considered related to the treatment or clinically significant. For this study, AEs will include events reported by the patient, as well as clinically significant abnormal findings on physical examination or laboratory evaluation. A new illness, symptom, sign or clinically significant

laboratory abnormality or worsening of a pre-existing condition or abnormality is considered an AE.

All AEs, including clinically significant abnormal findings on laboratory evaluations, regardless of severity, will be followed until satisfactory resolution. Serious adverse events that occur more than 30 days after the last administration of investigational agent/intervention and have an attribution of at least possibly related to the agent/intervention should be recorded and reported as per section **8.2**.

8.1.2 Suspected Adverse Reaction

Suspected adverse reaction means any adverse event for which there is a reasonable possibility that the drug caused the adverse event. For the purposes of IND safety reporting, ‘reasonable possibility’ means there is evidence to suggest a causal relationship between the drug and the adverse event. A suspected adverse reaction implies a lesser degree of certainty about causality than adverse reaction, which means any adverse event caused by a drug.

8.1.3 Unexpected Adverse Reaction

An adverse event or suspected adverse reaction is considered “unexpected” if it is not listed in the investigator brochure or is not listed at the specificity or severity that has been observed; or, if an investigator brochure is not required or available, is not consistent with the risk information described in the general investigational plan or elsewhere in the current application.

“Unexpected”, also refers to adverse events or suspected adverse reactions that are mentioned in the investigator brochure as occurring with a class of drugs or as anticipated from the pharmacological properties of the drug, but are not specifically mentioned as occurring with the particular drug under investigation.

8.1.4 Serious

An Unanticipated Problem or Protocol Deviation is serious if it meets the definition of a Serious Adverse Event or if it compromises the safety, welfare or rights of subjects or others.

8.1.5 Serious Adverse Event

An adverse event or suspected adverse reaction is considered serious if in the view of the investigator or the sponsor, it results in any of the following:

- Death,
- A life-threatening adverse drug experience
- Inpatient hospitalization or prolongation of existing hospitalization
- Persistent or significant incapacity or substantial disruption of the ability to conduct normal life functions
- A congenital anomaly/birth defect.
- Important medical events that may not result in death, be life-threatening, or require hospitalization may be considered a serious adverse drug

experience when, based upon appropriate medical judgment, they may jeopardize the patient or subject and may require medical or surgical intervention to prevent one of the outcomes listed in this definition.

8.1.6 Disability

A substantial disruption of a person's ability to conduct normal life functions.

8.1.7 Life threatening Adverse Drug Reaction

Any adverse event or suspected adverse reaction that places the patient or subject, in the view of the investigator or sponsor, at immediate risk of death from the reaction as it occurred, i.e., it does not include a reaction that had it occurred in a more severe form, might have caused death.

8.1.8 Protocol Deviation (NIH Definition)

Any change, divergence, or departure from the approved research protocol.

8.1.9 Protocol Non-compliance (NIH Definition)

The failure to comply with applicable NIH Human Research Protections Program (HRPP) policies, IRB requirements, or regulatory requirements for the protection of human research subjects.

8.1.10 Unanticipated Problem

Any incident, experience, or outcome that:

- Is unexpected in terms of nature, severity, or frequency in relation to
 - (a) the research risks that are described in the IRB-approved research protocol and informed consent document; Investigator's Brochure or other study documents, and
 - (b) the characteristics of the subject population being studied; **AND**
- Is related or possibly related to participation in the research; **AND**
- Suggests that the research places subjects or others at a *greater risk of harm* (including physical, psychological, economic, or social harm) than was previously known or recognized

8.2 NCI-IRB REPORTING

8.2.1 NCI-IRB Expedited Reporting of Unanticipated Problems and Deaths:

The Protocol PI will report to the NCI-IRB:

- All deaths, except deaths due to progressive disease
- All Protocol Deviations
- All Unanticipated Problems
- All serious non-compliance

Reports must be received by the NCI-IRB within 7 working days of PI awareness via iRIS.

8.2.2 NCI-IRB Requirements for PI Reporting at Continuing Review

The protocol PI will report to the NCI-IRB:

1. A summary of all protocol deviations in a tabular format to include the date the deviation occurred, a brief description of the deviation and any corrective action.
2. A summary of any instances of non-compliance
3. A tabular summary of the following adverse events:
 - All Grade 2 **unexpected** events that are possibly, probably or definitely related to the research;
 - All Grade 3 and 4 events that are possibly, probably or definitely related to the research;
 - All Grade 5 events regardless of attribution;
 - All Serious Events regardless of attribution.

NOTE: Grade 1 events are not required to be reported.

8.3 DATA AND SAFETY MONITORING PLAN

Clinical Trial Monitoring Plan

Data will be entered in C3D by the data manager assigned to the protocol. The research nurse will verify 100% of the e-CRFs for one of the first 3 patients enrolled. Subsequent monitoring will be conducted by the Research Nurse as described in the table below. Any significant discrepancies will be discussed with the PI and the study team and a corrective action plan will be drafted and shared with the team. AEs on all patients are discussed at the weekly team meeting to assess over all safety and to ensure that all reporting requirements are met.

*Based on expected accrual, 25% of enrolled patients will be monitored.

Time of year	Evaluation	# of records monitored
Quarterly	Compare all fields of the following e-CRFs to the source documentation: Eligibility, Surgical Procedure, Course Assessment, Adverse Events, Off Treatment	3-5 study patients

Careful evaluation to ascertain the toxicity and clinical response will be performed. The principal investigator will monitor the data and toxicities to identify trends quarterly. The principal investigator will be responsible for revising the protocol as needed to maintain safety.

9 PHARMACEUTICAL INFORMATION

9.1 VALPROIC ACID - DEPAKOTE

Refer to package insert for additional information

9.1.1 Source

Valproic acid will be purchased from commercial sources by the NIH Clinical Center Pharmacy.

9.1.2 Formulation and preparation

Valproic Acid tablets are for oral administration. Valproic acid tablets are supplied in three dosage strengths containing divalproex sodium equivalent to 125 mg, 250 mg, or 500 mg of valproic acid.

9.1.3 Stability and storage

Store tablets below 86°F (30°C).

9.1.4 Administration procedures

Valproic acid will be given orally, twice daily with or without food

9.1.5 Incompatibilities - Potentially significant drug interactions have been reported with Amitriptyline/Nortriptyline, Carbamazepine/carbamazepine, Clonazepam, Diazepam, Ethosuximide, Lamotrigine, Phenobarbital, Primidone, Phenytoin, Tolbutamide, Warfarin, and Zidovudine.

9.1.6 Toxicity

- Hepatotoxicity
- Teratogenicity in the fetus of pregnant women. At high doses (>90mg/kg/day), valproic acid has been shown to reduce spermatogenesis and induce testicular atrophy in dogs.
- Hyperammonemia has been reported independent of abnormal liver function tests.
- CNS depression and somnolence. Because of the potential interactions of valproic acid with other CNS depressants, alcohol will be prohibited while patients are on the study. If a patient does drink alcohol, he or she will be removed from the study.
- Nausea, vomiting, anorexia, increases appetite and indigestion
- Thrombocytopenia
- Pancreatitis

9.2 LIOTHYRONINE SODIUM, CYTOMEL

Refer to package insert for additional information

9.2.1 Source

Cytomel will be purchased from commercial sources by the NIH Clinical Center Pharmacy.

9.2.2 Formulation and preparation

Cytomel tablets are for oral administration. Cytomel tablets are supplied in three dosage strengths 5 mg, 25 mg, or 50 mg.

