3.5 PHASE 2 WEEKS 11-16

3.5.1 Schedule 1 - Patients who exhibit an increased radioiodine uptake on Thyrogen scan post valproic acid therapy at week 10.

- Week 11:
 - Discontinue Levothyroxine
 - Begin Cytomel for 4 weeks (25 micrograms twice a day)
 - Continue valproic acid for a total of 16 weeks

Note: medication will be dispensed following review of Thyrogen scan
- Week 12 - may be performed by their primary physicians
 - Physical exam including ECOG status
 - CBC with differential, platelets, BUN, creatinine, total protein, total bilirubin, ALT, AST, ALKP, amylase, ammonia, albumin and b-HCG (if applicable).
 - Toxicity assessment, pill count, and review of diary
- Week 14: may be performed by their primary physicians
 - Physical exam including ECOG status
 - CBC with differential, platelets, BUN, creatinine, total protein, total bilirubin, ALT, AST, ALKP, amylase, ammonia, albumin and b-HCG (if applicable).
 - Toxicity assessment, pill count, and review of diary
 - Stop Taking Cytomel.
 - Begin low iodine diet.
- Week 16:
 - Measure TSH, Tg and 24 hour urinary iodine.
 - I-131 Ablative treatment {refer to Section 3.6}.
 - Physical exam including ECOG status
 - CBC with differential, platelets, BUN, creatinine, total protein, total bilirubin, ALT, AST, ALKP, amylase, ammonia, albumin and b-HCG (if applicable).
 - Toxicity assessment, pill count, and review of diary
- Week 17:
 - Post ablation RAI scan {5 days (+/- 2 days) following administration of 131-I}.
 - Ultrasound of the neck
 - MRI or CT of the neck and chest
 - FDG-PET scan
 - Resume Levothyroxine (pre study dose) .

- Stop valproic acid end of week 17
- Toxicity assessment, pill count, and review of diary
- Health Related Quality of Life HRQOL) form completion

3.5.2 Schedule 2 – patients who do not exhibit an increased radioiodine uptake on Thyrogen scan post valproic acid therapy at week 10

- Week 11:
 - Maintain valproic acid dose
- **Note:** medication will be dispensed following review of the Thyrogen scan.
- Week 12:
 - Physical exam including ECOG status
 - CBC with differential, platelets, BUN, creatinine, total protein, total bilirubin, ALT, AST, ALKP, amylase, ammonia, albumin and b-HCG (if applicable).
 - Serum valproic acid levels.
 - Toxicity assessment and review of diary
- Week 14: may be performed by local physician
 - Physical exam including ECOG status

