9.2.4 Administration procedures

Cytomel will be given orally, once daily with or without food

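### Liothyronine is scheduled twice a day in section 3.5.1 but once daily in section 9.2.4, and the tablet strengths in section 9.2.2 are printed in a unit that does not fit the scheduled dose

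*Protocol*

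**What the plan says.** Three places in the protocol state a dose, strength or frequency for liothyronine (Cytomel).

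- Section 3.5.1 (Schedule 1, for patients whose radioiodine uptake has increased at week 10) stops levothyroxine at week 11 and continues: "Begin Cytomel for 4 weeks (25 micrograms twice a day". Under week 14 it instructs: "Stop Taking Cytomel".
- Section 9.2.2 gives the supply: "Cytomel tablets are supplied in three dosage strengths 5 mg, 25 mg, or 50 mg".
- Section 9.2.4 gives the administration: "Cytomel will be given orally, once daily with or without food". It names no amount.

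Section 9.2 also refers to the package insert, and section 9.2.1 says that the Clinical Center pharmacy buys the drug commercially. Neither statement settles the dose or frequency for this study.

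**The concern.** The treatment schedule and the pharmaceutical section should lead any reader to the same regimen. Here they do not. One gives two administrations a day and the other gives one, and the tablets listed are in milligrams while the dose is in micrograms.

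What is at stake is dosing safety and consistent conduct. Two people following different sections of the same approved protocol could instruct patients differently, and each could regard the other's regimen as a protocol deviation. Section 8.2.1 sends all deviations to the IRB within 7 working days. Section 9.2.6 identifies the effects of overdosage as the main adverse reactions to this drug, so an unclear unit or frequency should not be left standing.

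**Working it through.** No sample-size or error-rate figure is involved. The check is a unit conversion and a side-by-side reading.

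**Inputs**
- Single dose 25 micrograms, twice a day (section 3.5.1).
- Tablet strengths printed as 5, 25 and 50 mg (section 9.2.2).
- Once daily, amount not given (section 9.2.4).
- 1 mg = 1000 micrograms.

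**Frequency**

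Daily total under section 3.5.1: 2 × 25 = 50 micrograms.

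Daily total under section 9.2.4: 1 × *x*, where *x* is not stated. The ratio of the two totals is 50 / *x*.
- Assuming *x* = 25 micrograms: 50 / 25 = 2, a two-fold difference.
- Assuming *x* = 50 micrograms: 50 / 50 = 1, the same daily total at a different frequency.

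The conflict in frequency is therefore certain. The difference in daily dose depends on an amount that section 9.2.4 does not give.

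**Unit, as printed**

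Ratio = tablet strength in micrograms / 25.

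| Printed strength | In micrograms | Ratio to the 25-microgram dose | Tablet fraction per dose |
|---|---|---|---|
| 5 mg | 5,000 | 200 | 1/200 |
| 25 mg | 25,000 | 1000 | 1/1000 |
| 50 mg | 50,000 | 2000 | 1/2000 |

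The factor of 1000 is the unit factor and applies to the 25 mg tablet against the single dose. For the other two strengths the ratio is 200 or 2000. No listed strength can supply the scheduled dose.

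**Comparison with the study drug**

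For valproic acid, the same two checks come out clean. Section 9.1.4 says twice daily, which agrees with the morning and evening dosing in section 3.2.1 from day 4 on. The 125, 250 and 500 mg strengths in section 9.1.2 can make up the scheduled 500 and 1000 mg doses. Section 9.2 fails both checks for liothyronine.

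**Timing against the endpoints**

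Liothyronine begins at week 11 and is stopped at week 14. The thyroglobulin and uptake components of response in section 5.2 are read at week 10, before it starts. The week-16 thyroglobulin measurement and I-131 treatment come after it has stopped.

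**The case against.** The strongest objection is to the unit. The text at hand was converted from PDF, and small unit symbols do not come through it reliably: the ammonia limit in section 3.9.1 reads mol/l with its prefix apparently missing, and the trough-level unit in section 1.3 is broken by a space. The numerals in section 9.2.2 would also fit the scheduled dose if they were in micrograms (25 / 5 = 5 tablets, 25 / 25 = 1, 25 / 50 = 1/2). Against this, the micro sign survives in the Precis, section 1.3 and section 3.2.3, and section 9.2.2 shows three identical, legible units. Neither side is conclusive, so the unit needs checking and cannot yet be called an error. This doubt does not reach the frequency conflict, which is in ordinary words in both places.

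Three stronger readings are tempting, and the protocol does not support them.

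- A reader might infer that patients could receive 1000 times the intended dose. The schedule spells out micrograms in words, the drug is a commercial product with a package insert, and a dose that cannot be made from the listed tablets would show itself at dispensing. The protocol also says only that the pharmacy purchases the drug, not that it dispenses from section 9.2.
- A reader might infer a two-fold difference in daily dose. That requires carrying 25 micrograms into section 9.2.4, which gives no amount.
- A reader might infer that the week-16 thyroglobulin value or the I-131 treatment is compromised. Liothyronine is stopped at week 14 under either frequency, and levothyroxine has been off since week 11, so this is not a period of planned TSH suppression. No effect is shown.

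It can also be said that this is a small inconsistency in the reference section for an adjunct drug given only to Schedule 1 patients. That is fair as to scale. It still concerns an operative dosing instruction.

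**Conclusion.** The concern holds in limited form. The protocol contradicts itself on liothyronine frequency: twice a day in section 3.5.1, once daily in section 9.2.4. This does not depend on how the PDF was converted. Under the stated assumption of 25 micrograms per dose in both places, the daily total is 50 or 25 micrograms.

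The unit in section 9.2.2 is a second, less certain point. As printed, the 25 mg tablet is 1000 times the single dose, but a lost symbol is possible.

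Both points are matters of dosing safety and internal consistency for Schedule 1 patients. Sample size, error rates and the week-10 response components are untouched. The protocol does not show which unit, strength or frequency is right, and no view on that is taken here. The correction should be made, but it is not a flaw in the trial's inference.

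**What to change.** Check the units in section 9.2.2 against the original protocol document and the supplied product. Then reconcile sections 3.5.1, 9.2.2 and 9.2.4 so that unit, strength and frequency agree, and state the amount per administration wherever a frequency is given. The clinical team and pharmacy must decide which statements stand.

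The cost is an edit of about two lines in section 9.2 or section 3.5.1, plus the check. No statistical section changes.
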